8.4.2. Other Reasons for Discontinuation of Study or Investigational Product

Subjects that discontinue investigational product are expected to continue in the study until the end of the study, and the study will only terminate at the time when the needed number of adjudicated events has accrued or at the discretion of the Sponsor. If a subject reaches an event, he or she should continue the regular visit schedule and continue taking investigational product as long as the Investigator assesses it as safe. Subjects who choose to discontinue investigational product prior to termination of the study need to also continue to follow the regular visit schedule

through to study closure. In general, subjects should be strongly encouraged to both stay on investigational product and remain in the study until study termination. Early termination procedures should only be conducted if the subject withdraws consent (See [Section 9.7.18](#) Early Discontinuation and/or Early Termination Procedures).

The following events are considered appropriate reasons for a subject to discontinue investigational product; however, these subjects are expected to continue in the study until study termination and the study will only terminate at the time when the needed number of adjudicated events has accrued (or at the discretion of the Sponsor):

- Subject begins treatment with commercially available OCA
- The Investigator or Sponsor considers that it is advisable or in the best interest of the subject.
- The occurrence of clinical or laboratory AEs considered by the Investigator to be clinically important safety concerns and related to study drug.
- Withdrawal of consent
 - Consent may be fully withdrawn (in which case the subject discontinues both investigational product and study visits and procedures).
 - Consent may be modified to discontinue study visits but allow semi-annual telephone contact.
 - Consent may be modified to discontinue study visits or semi-annual telephone contact but allow continued access to medical records to assess for potential adjudicated hepatic and/or cardiovascular events.

Subjects who undergo a liver transplant during the course of the study must discontinue investigational product and discontinue the study visit schedule. However, these subjects should be encouraged to consent to the semiannual telephone contact and/or continued record review only to allow for secondary outcome events data to be collected.

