Early Termination	Discontinued	Withdrawn	No additional visits except EOT/EOS	Combined Visit, Completed as close as possible to last dose IP	
Treatment Discontinuation^b	Discontinued	Active	Regular Visit Schedule	Complete as close as possible to last dose IP	Complete at Final study visit
	Discontinued	Semiannual contact ^c	Telephone contact every 6 months (± 2 weeks)	Combined Visit, Completed as close as possible to last dose IP	
	Discontinued	Record review only ^c	Record review only	Combined visit Completed as close as possible to last dose IP	
Sponsor Termination	Discontinued	N/A	No additional visits except EOT/EOS	Combined visit Completed as close as possible to last dose IP	
Pregnancy	Interrupted	Retained	Regular Visit Schedule	Complete as close as possible to last dose IP	Complete at Final study visit
	Discontinued	Complete per the above scenarios - Early Termination or Treatment Discontinuation			
Lost to Follow-up	Discontinued	LTF	None	Unable to complete due to LTF status	

EOS = end of study; EOT = end of treatment; IP = investigational product

^a Refer to [Section 7.1.2](#) Schedule of Study Procedures, [Table 2](#) for all procedures and evaluations required at the End of Treatment and End of Study Visits.

^b Includes initiation of commercially available OCA.

^c Outcomes data to be discussed or collected include data related to adjudicated hepatic and cardiovascular event-related data. No additional data (e.g. AE, concomitant medication, etc) data will be collected, except as indicated in [Section 12.1.7](#).

Some assessments noted below may be omitted if they have been completed within the 6 months (or the timeframe otherwise specified) and so long as safety issues do not warrant repeat testing.

Prior to the EOT/EOS Visit:

If possible to do before the visit, when scheduling the EOT/EOS visit, reiterate dosing instructions and advise the subject:

- If applicable, NOT to take investigational product on the morning of the next visit, and
- To bring the investigational product bottle(s); if applicable, s/he will dose at the clinic, and

- To fast overnight (at least 8 hours) prior to the next visit. Fasting is required prior to all study visits, but water is permitted.

During the EOT/EOS Visit:

- Perform a physical examination (including smoking and alcohol consumption habits).
- Perform assessment for calculation of Mayo Risk Score.
- Perform assessments for calculation of Child-Pugh Score.

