Hematology	Hemoglobin, hematocrit, white blood count with differential, neutrophils, lymphocytes, monocytes, eosinophils, basophils, platelets, red blood cell count (including MCV, MCH, MCHC)
Coagulation	Prothrombin time (PT), partial thromboplastin time (PTT), international normalized ratio (INR)
Urinalysis	pH, specific gravity, total protein, glucose, ketones, bilirubin, blood, microscopic exam, urobilinogen, albumin, creatine, leucocytes, nitrates, albumin/creatinine ratio (if positive)
Biomarkers of Hepatic Fibrosis and/or Inflammation	IgM, C-reactive protein (CRP), TNF- α , FGF-19, CK-18, ELF, and others as determined during course of study
Measurement of Liver Fibrosis	Fibroscan
Bone Density Assessment	DEXA
Genetics	DNA including single-nucleotide polymorphisms (SNPs) that may be involved in PBC; RNA
Blood Sample for Future Analysis	PBC autoantibodies and other cytokines and interleukins TBD
Other	OCA (parent and conjugates [glyco and tauro]) and C4

The Investigator should manage subjects with clinically significant lipoprotein abnormalities using local standard of care procedures as appropriate after assessing the individual subject's total cardiovascular risk profile.

Urine-based β -hCG pregnancy tests will be performed in female subjects of childbearing potential per protocol specified visits. If a urine pregnancy test is positive, a serum pregnancy test must be performed to confirm the result. If positive, the Sponsor must be notified and the subject will be followed, as outlined in [Section 12.1.9](#) through pregnancy outcome.

MELD scores, Child-Pugh score, and MRS will be calculated at screening, and at quarterly (MELD and Child-Pugh scores) or semi-annual (MRS) visits based on serum chemistry and coagulation.

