13.1.10.1. Time to Event Endpoints

For the time to event analyses, subjects who do not experience an event will be censored at the time of their last contact. Subjects with no data after randomization will be considered to have an event on Day 1 (first day of investigational product dosing).

For analyses of the percentage of subjects with an event, subjects with no data after randomization will be considered to have an event.

All time to event endpoints include only adjudicated events. Sensitivity analyses may consider all events regardless of adjudication. Events with discrepant adjudication will be analyzed using both results.

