13.1.11. Multiple Comparisons/Multiplicity

The key secondary efficacy endpoints are as follows:

- Time to MELD score ≥ 15
- Time to first occurrence of liver transplant or death (all-cause)
- Change from Baseline in total bilirubin at end of study
- Change from Baseline in ALP at end of study

The hypothesis testing of key secondary analyses will compare placebo and OCA and will be conducted in a sequential closed testing gate-keeping procedure (in the order in which the key secondary endpoints are stated above), provided that the primary efficacy endpoint comparison is statistically significant in favor of OCA. If the primary comparison is not statistically significant then comparison of the secondary endpoints will be considered as descriptive and exploratory. This procedure controls the study-wise type I error.

- First (step 1) placebo and OCA will be compared with respect to the primary efficacy endpoint. If the comparison achieves statistical significance at 2-sided 0.05 level in favor of OCA group, then
- The time to MELD score ≥ 15 will be compared between placebo and OCA (step 2). If the comparison achieves statistical significance at 2-sided 0.05 level in favor of OCA group, then
- The time to liver transplant or death (all-cause) will be compared between placebo and OCA (step 3). If the comparison achieves statistical significance at 2-sided 0.05 level in favor of OCA group, then
- Change from Baseline in total bilirubin will be compared between placebo and OCA (step 4). If the comparison achieves statistical significance at 2-sided 0.05 level in favor of OCA group, then
- Change from Baseline in ALP at the end of study will be compared between placebo and OCA (step 5).

If at any step defined above the comparison is not statistically significant at the 2-sided 0.05 level then the remaining comparisons in the stated hierarchy will be considered descriptive and exploratory. The study-wise type I error will be maintained with the above closed procedure.

Additional efficacy endpoints will be analyzed; however, hypothesis tests will be applied for descriptive and exploratory purposes only.

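### Time to MELD ≥15 is censored at last contact, so time after MELD stops being measured counts as MELD-free; the bias depends on an imbalance between arms that the protocol does not give

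*Protocol*

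**What the plan says.** All references are to the current protocol text (Version 3).

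- **Censoring.** Section 13.1.10.1 states for time-to-event analyses that "subjects who do not experience an event will be censored at the time of their last contact". It makes no exception by endpoint. Its sensitivity analyses concern adjudication, not the censoring date.
- **How MELD is obtained.** Section 12.2.7 has MELD calculated at screening and at quarterly "visits based on serum chemistry and coagulation".
- **Who may leave visits but stay in contact.** Section 8.4.2 allows: "Consent may be modified to discontinue study visits but allow semi-annual telephone contact". A further option keeps access to medical records only. Table 7 (Section 9.7.18) gives the telephone group a combined end-of-treatment and end-of-study visit near the last dose, then "Telephone contact every 6 months". Its footnote c describes what is gathered: "Outcomes data to be discussed or collected include data related to adjudicated hepatic and cardiovascular event-related data".
- **Transplant.** Section 8.4.2 also says: "Subjects who undergo a liver transplant during the course of the study must discontinue investigational product and discontinue the study visit schedule". These subjects are encouraged to accept telephone contact and/or record review.
- **Role of the endpoint.** Time to MELD ≥15 is the first key secondary endpoint and step 2 of the hierarchy (Section 13.1.11), tested at two-sided 0.05 with the primary's stratified log-rank and Cox methods (Section 13.1.4).

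**The concern.** Last contact is a sensible censoring date for death or transplant, because a call or a chart can establish either. MELD ≥15 is a laboratory threshold that the trial looks for systematically only when chemistry and coagulation samples are taken. A subject who gives up visits at year 2 and answers calls until year 7 stays in the MELD risk set for five years in which the trial has no scheduled way to see the event.

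Two things follow. Kaplan-Meier MELD-free survival is too high in any arm that contains such time. If the amount of such time differs between arms, the arm with more of it shows a lower MELD rate for that reason alone. At stake is a confirmatory test on which steps 3 to 5 depend. MELD ≥15 is also a component of the primary composite. The effect should be smaller there, because deaths, transplants and hospitalised events can be learned by telephone.

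**Working it through.** **The plan's own figure.** For the primary composite, events = 4(1.96 + 0.8416)² / (ln 0.60)² = 31.40 / 0.2609 = 120.3, so 121, with 80.2% power. The stated 121 is reproduced. It does not bear on MELD alone: the protocol gives no MELD hazard and no rate of leaving visits.

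**Inputs from the protocol.** 350 subjects, 1:1, 2 years' accrual and 6 years' follow-up, so 6 to 8 years per subject.

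**Assumptions.** MELD hazard λ = 0.045 per year, about half the composite hazard of ln 2 / 8 = 0.0866. Constant rate g of moving to telephone-only follow-up, independent of MELD risk. No MELD event found after the move. Death as a competing event is ignored.

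**Person-time check.** For follow-up F = 7 years (the midpoint), expected time at risk while on visits is V = (1 − e^(−(λ+g)F)) / (λ+g). Expected telephone time counted as MELD-free is P = g/(λ+g) × (F − V). Expected events are λV. Under last-contact censoring the apparent rate is λV/(V+P), so with a true hazard ratio of 1.0 the apparent ratio is the OCA share V/(V+P) divided by the placebo share.

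- OCA, g = 0.04: V = (1 − e^(−0.595))/0.085 = 5.276; P = (0.04/0.085)(7 − 5.276) = 0.811; share 0.867.
- Placebo, g = 0.02: V = (1 − e^(−0.455))/0.065 = 5.624; P = (0.02/0.065)(7 − 5.624) = 0.423; share 0.930.
- Ratio 0.867/0.930 = 0.93.

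Other rates are in the table. The last column is the simulated one-sided, stand-alone rate of significance in favour of OCA (nominal 2.5%).

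| OCA / placebo, per year | Off visits by year 6, 1 − e^(−6g) | Apparent HR (true 1.0) | False significance for OCA |
|---|---|---|---|
| equal, 3% / 3% | 16% / 16% | 1.00 | about 2.5% |
| 4% / 2% | 21% / 11% | 0.93 | about 5% |
| 6% / 3% | 30% / 16% | 0.90 | about 7% |
| 10% / 5% | 45% / 26% | 0.85 | about 10% |
| 2% / 4% | 11% / 21% | 1.07 | about 1% |

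**Other assumptions.** Take 10% of placebo and 30% of OCA subjects as telephone-only by year 6. A true ratio of 1.00 then appears as 0.86 to 0.87 for MELD hazards from 0.02 to 0.0866, and a true 0.60 appears as 0.52. False significance for OCA is about 8% (hazard 0.04) to 14% (hazard 0.0866). With the split reversed, the ratios are 1.15 to 1.17 and about 0.70.

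**Kaplan-Meier level.** At λ = 0.045 the true 6-year MELD-free proportion is e^(−0.27) = 76.34%. Under last contact it appears as 1 − λ/(λ+g) × (1 − e^(−6(λ+g))): 77.64% at g = 0.02 and 81.97% at g = 0.10. That is 1.3 to 5.6 points too high, and it arises even when the arms are equal.

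**After the fix.** Censoring at the last MELD assessment returned the true hazard ratio to within about 0.01, with null error of 2% to 3% per side, in every scenario.

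**The case against.** Several points on the other side stand.

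- **Telephone-only follow-up is not the default.** Sections 7.4.2, 8.4.2 and 9.2.1 expect subjects who stop investigational product, including those who start commercial OCA, to keep the regular visit schedule. Leaving visits takes a documented change of consent (Section 9.7.2). The group may be small.
- **The direction is unknown.** A reader might infer that OCA gains, because pruritus is its main adverse effect. The protocol nowhere links pruritus to leaving visits. The only exit from visits that it requires after an outcome is transplant. If OCA works, that exit is more common on placebo, which would bias against OCA.
- **Ascertainment is not zero.** Hepatic event data may be gathered after visits end, and adjudication may use hospital records (Section 13.4). Some MELD values may surface, above all under record review. The calculations assume none do.
- **The error rates are stand-alone.** Step 2 is tested only after a significant primary result, so they are not study-wise rates. A reader might infer that type I error at step 2 is simply uncontrolled; the documents do not support that without an imbalance that they do not state.
- **A SAP may refine the date.** It may, but the protocol does not leave this open: it states one rule, and a SAP that follows it would repeat the problem.

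**Conclusion.** The point holds as a defect in a stated rule with consequences of unknown size. Section 13.1.10.1 counts time as MELD-free after MELD has ceased to be systematically observed. This overstates MELD-free survival wherever such time exists, and it biases the step 2 hazard ratio towards the arm with more of it.

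The illustrative two-fold imbalances move a true ratio of 1.0 to between 0.93 and 0.85, or to 1.07 when 4% and 2% are reversed. The upper end needs about 45% of the OCA arm off visits by year 6, which nothing in the protocol suggests. The rates, the MELD hazard, the independence of leaving from MELD risk and the zero ascertainment after leaving are all assumptions. A claim that the rule favours OCA, or that it breaks error control as things stand, goes beyond the documents. The correction is still worth making before unblinding, because a change to the censoring date afterwards would look driven by the data.

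**What to change.** In Section 13.1.10.1, and in the SAP to match:

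- For time to MELD ≥15, censor event-free subjects at the last visit with evaluable bilirubin, creatinine and INR. Count only MELD events within that period of scheduled assessment. Limiting events as well as censoring matters: otherwise late events found by chance would count while the matching event-free time was removed, a bias the other way.
- Put MELD events found later by telephone or record review in a sensitivity analysis.
- Keep last contact for the death and transplant endpoints.
- Keep the present rule for the primary composite, and add one sensitivity analysis censored at the last MELD assessment.

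The cost is a few sentences and no change to any study procedure. Some event-free person-time and a few late MELD events leave the main MELD analysis. That analysis then relies on the missing-at-random assumption that Section 13.1.10 already makes. It does not settle death or transplant before MELD ≥15, which remain competing events.

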13.1. Efficacy Analysis

13.1.1. Analysis Populations

The following subject populations will be evaluated and used for presentation and analysis of the data:

- The Randomized Population will include all randomized subjects.
- The Intent-to-Treat (ITT) Population will include all randomized subjects who receive any amount of investigational product (OCA or placebo). The ITT Population will be the primary population used for efficacy analyses. Treatment assignment will be based on the randomized treatment.
- The Safety Population will include all subjects who received any amount of investigational product (placebo or OCA). The Safety Population will be the primary population used for safety analyses. Treatment assignment will be based on the treatment actually received.
- The PK population will include all OCA subjects who have at least one confirmed fasted analyzable sample. Subjects must have been fasting for approximately 8 hours prior to the visit and must not have any major protocol deviations that potentially affect exposure levels. The PK population will be used for OCA PK analyses.
- The Overall Historical Control Population will include subjects from the United Kingdom (UK) -PBC Group and Global PBC Study Group databases with demonstrated comparability to randomized subjects in this clinical study (747-302) with respect to both subject characteristics and disease progression.
- The UK-PBC Historical Control Population will include subjects from the UK-PBC Group databases with demonstrated comparability to randomized subjects in this clinical study (747-302) with respect to both subject characteristics and disease progression.
- The Global PBC Historical Control Population will include subjects from the Global PBC Study Group database with demonstrated comparability to randomized subjects in this clinical study (747-302) with respect to both subject characteristics and disease progression.

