13.1.3. Primary Efficacy Analysis

The primary efficacy endpoint will be the time to first occurrence of one of the following post-randomization:

- Death (all-cause)
- Liver transplant
- MELD score ≥ 15
- Hospitalization (as defined by a stay of 24 hours or greater) for new onset or recurrence of:
 - Variceal bleed
 - Encephalopathy (as defined by a West Haven score of ≥ 2)
 - Spontaneous bacterial peritonitis (confirmed by diagnostic paracentesis)
- Uncontrolled ascites (diuretic resistant ascites requiring therapeutic paracentesis at a frequency of at least twice in a month).
- Hepatocellular carcinoma confirmed by 2 complimentary imaging modalities.

The primary efficacy analysis will compare randomized OCA to randomized placebo with respect to the primary efficacy endpoint using the ITT population. Only adjudicated events will be included in analyses. The 2 treatment groups will be compared using the log rank test stratified by the randomization stratification factor. Kaplan-Meier (KM) estimates of the distribution of the time-to-event will be tabulated and graphed by treatment group. The tabulation will include the KM estimate of the medians and corresponding 95% confidence intervals (CIs), if the medians can be estimated. The number and percent of subjects censored and with events will be presented. The hazard ratio and 95% CI will be determined based on a Cox regression model stratified by randomization strata to estimate the magnitude of the effect.

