13.1.10. Handling of Dropouts or Missing Data

Subjects who discontinue investigational product are expected to continue in the study until study termination.

Missing data will be assumed to be missing at random. In order to determine the effect of missing data on the analysis, efficacy endpoints will be analyzed using different methods of imputation as described below.

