13.4. Adjudication Committees

All suspected liver-related clinical outcomes, MACE/Expanded MACE, and drug-related hepatic injury events that occur after administration of the first dose of investigational product will be reviewed by the following blinded adjudication committees, depending on event type, before inclusion in any analysis. The 3 committees and event types they are responsible for adjudicating are as follows:

- Cardiovascular Adjudication Committee (CAC): Adjudicates all suspected MACE, including all deaths
- Hepatic Outcomes Committee: Adjudicates all deaths and suspected liver-related outcomes
- Hepatic Safety Committee: Adjudicates all suspected drug-related hepatic injury events

Each adjudication committee will have a charter that documents the reporting of events by the study site, definition of the suspected events to be adjudicated, supply of source documentation to the committee, entire data flow and process from committee membership, review of the events by the committee, reporting of the final assessment, and the working procedures of the committee.

The adjudication committee members will include experts with relevant adjudication experience; they will not be involved in the study as Investigators, DMC members, or consultants. Any candidate found to have a conflict or whose name is listed on the FDA debarment list is not offered membership. Conflicts of interest are assessed regularly, and if members are found to have a new conflict of interest they will be replaced.

The adjudication of suspected events will be based on available source documentation, including but not limited to individual clinical study data, hospital records, histology, discharge summaries, and/or death certificates. The adjudication committees will not receive any individual subject treatment or site-specific information. The assessment of events will be conducted in compliance with study-specific procedures, manuals, good clinical practice (GCP), and all other applicable regulatory requirements, including the archiving of essential documents.

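### Scoring subjects with no post-randomization data as Day 1 events contradicts the protocol's rule that only adjudicated events are analysed

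*Protocol*

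**What the plan says.** Section 13.1.10.1 of the protocol opens with an ordinary censoring rule for the time-to-event analyses: "subjects who do not experience an event will be censored at the time of their last contact". The next sentence makes an exception: "Subjects with no data after randomization will be considered to have an event on Day 1 (first day of investigational product dosing"). A parallel sentence covers proportions: "For analyses of the percentage of subjects with an event, subjects with no data after randomization will be considered to have an event". None of these is described as a sensitivity analysis. The neighbouring sections 13.1.10.2 and 13.1.10.3 do label their alternatives that way, and 13.1.10.1 itself keeps the term for an analysis of events regardless of adjudication.

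The same section also says "All time to event endpoints include only adjudicated events". Section 13.1.3 says of the primary analysis: "Only adjudicated events will be included in analyses". Section 13.4 says suspected events arising after the first dose "will be reviewed by the following blinded adjudication committees, depending on event type, before inclusion in any analysis".

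The primary efficacy population is defined in section 13.1.1: "The Intent-to-Treat (ITT) Population will include all randomized subjects who receive any amount of investigational product (OCA or placebo"). Under section 9.7.7, dosing begins on Day 1, the day after the randomization visit.

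**The concern.** A subject who disappears after the Day 0 visit has no event and no source documents for a committee to review. The Day 1 rule nevertheless enters that subject as a primary endpoint event at the earliest possible time. A programmer cannot obey this rule and the adjudicated-only rule together, and the protocol does not say which prevails. If the choice is left until after unblinding, it could be driven by the result.

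The rule covers every time-to-event endpoint. The same subject would be scored on Day 1 for MELD ≥15 and for transplant or death, which are the first two key secondary tests in the hierarchy of section 13.1.11.

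The ITT definition adds a second difficulty. Evidence of dosing, such as a diary, a tablet count or a telephone report, is itself post-randomization data. On a strict reading, a subject with no data therefore has no documented dose and falls outside ITT, which leaves the rule empty for the primary analysis. If such subjects are kept in, that goes against the definition.

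**Working it through.** **Inputs.** From section 13.1.2: hazard ratio 0.60, two-sided 5% log-rank test, 1:1 allocation, 121 events, 80% power, about 350 subjects. The number of no-data subjects, m, is not in the protocol. I assume m = 0 to 10, up to about 3% of 350.

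**The plan's own figure.** The Schoenfeld formula gives 4 × (1.960 + 0.842)² / (ln 0.60)² = 120.3, rounded up to 121. With 121 events, E(Z) = √(121/4) × |ln 0.60| = 5.5 × 0.5108 = 2.810, and power = Φ(2.810 − 1.960) = 80.2%. The 121 is reproduced.

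**Balanced imputed events, added to the 121 adjudicated ones.** Each adds 1/4 to the log-rank variance and, when balanced, no signal:

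E(Z) = (121/4) × 0.5108 / √((121 + m)/4)

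- m = 0: 15.45 / 5.50 = 2.81; power 80.2%; expected hazard ratio 0.60
- m = 4: 15.45 / 5.59 = 2.76; power 78.9%; expected hazard ratio 0.61
- m = 10: 15.45 / 5.72 = 2.70; power 77.0%; expected hazard ratio 0.62

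The loss is about 1 to 3 percentage points.

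**Imbalanced imputed events.** On Day 1 about half of those at risk are in each arm, so each net case moves the score by about 0.5. With the variance held at 121/4 = 30.25, the shift in Z is 0.5/5.5 = 0.091 per net case.

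- Three net cases in OCA: E(Z) = 2.810 − 0.273 = 2.537; power = Φ(0.577) = 71.8%. Including the added variance, 124/4 = 31, it is 70.7%.
- Four in OCA, with added variance: 67.2%.
- Four in placebo with no true effect, with added variance: the chance of a false OCA win, given that particular split, is 5.5% instead of 2.5%.

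**Simulation check.** 350 subjects, 1,500 runs, exponential survival, 6 to 8 years of follow-up. About 133 events are expected, so the starting power is slightly higher. Power was 82.3% with none imputed, 81.7% with 2 per arm, 79.5% with 5 per arm, and 71.9% with 4 in OCA only. With no true effect, false OCA wins were 2.7% with none imputed and 5.1% with 4 in placebo only. Direction and rough size agree with the formulas.

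**After the fix.** Subjects censored at the start of follow-up add no events and no variance, so the 121 adjudicated events keep 80.2% power.

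**The case against.** The best defence is that the rule hardly touches anything. The primary analysis uses ITT, ITT requires dosing, and 13.1.10.1 adds nobody to that population. Several other routes to data would also have to fail: section 9.7.8 allows Month 1 contact by telephone with samples taken elsewhere, section 8.4.4 requires efforts to reach lost subjects, and section 8.4.2 allows telephone-only or record-review follow-up. This stands, and it limits the size of the problem. It does not remove the contradiction.

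Four stronger readings are tempting, but the documents do not support them.

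- *The rule inflates the type I error.* The 5.5% above is conditional on all the cases falling in the placebo arm. In a blinded 1:1 trial, subjects lost before producing any data are exchangeable between arms under the null, so the overall 5% level is not shown to be exceeded. Inflation would need treatment-related loss with no data at all, and nothing in the protocol indicates that.
- *It is unclear whether imputed events count toward the 121.* Sections 7.1, 7.2, 7.5 and 13.1.2.1 all define the target as adjudicated events, so they do not count.
- *The rule flatly contradicts missing at random.* Section 13.1.10 does say "Missing data will be assumed to be missing at random", but its next sentence announces several imputation methods to examine the effect of missing data. A worst-case method fits under that sentence. The defect is the absent label.
- *The primary analysis should move to the Randomized Population.* That is a separate design change. Section 13.4 sends only events after the first dose to adjudication, so undosed subjects' events would have no adjudication route.

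**Conclusion.** The contradiction is real and is enough by itself to require a change: 13.1.10.1 creates events that cannot be adjudicated, while the same section, 13.1.3 and 13.4 exclude them. The mismatch with the ITT definition is secondary and supports the same change.

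The expected size is modest. With an assumed 4 to 10 balanced cases on top of 121 adjudicated events, power falls from 80.2% to 78.9% to 77.0%. A drop to about 72%, or a raised chance of a false OCA win, arises only if the cases cluster in one arm. These figures rest on the protocol's hazard ratio of 0.60 and on assumed counts. The 121-event calculation itself is correct.

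**What to change.** In section 13.1.10.1, replace the Day 1 sentence with: *Subjects with no post-randomization data are censored at the start of follow-up (randomization/Day 1).* Either date gives the same log-rank result, because no event precedes it.

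Change the percentage sentence so that these subjects are not counted as events, and say whether they stay in the denominator. Keeping them there as non-events is also an assumption.

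Keep the Day 1 scoring, if wanted, as a worst-case sensitivity analysis labelled as such and as an explicit exception to the adjudicated-only rule. Leave the primary population as it is.

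The cost is two sentences in the protocol, carried into the SAP before unblinding. No new data are needed and patients are not affected.
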